## LIST OF ABBREVIATIONS

AE	Adverse Event/Adverse Experience
ASA	American Society of Anesthesiologists
ASES	American Shoulder and Elbow Surgeons Standardized Shoulder Assessment Form
C-ISB	Continuous Interscalene Nerve Block
CFR	Code of Federal Regulations
CRF	Case Report Form
DSMB	Data and Safety Monitoring Board
FDA	Food and Drug Administration
GCP	Good Clinical Practice
HIPAA	Health Insurance Portability and Accountability Act
IB	Investigator's Brochure
IRB	Institutional Review Board
LANSS	Leeds Assessment of Neuropathic Symptoms and Signs
LAST	Local Anesthetic Systemic Toxicity
LB-SISB	Liposomal Bupivacaine Single injection interscalene blockade
NRS	Numeric Rating Scale
OBAS	Overall Benefit of Analgesic Score
OME	Oral Morphine Equivalents
PACU	Post-anesthesia Care Unit
PHI	Protected Health Information
PI	Principal Investigator
POD	Postoperative Day
QoR-15	Quality of Recovery 15-item short form patient survey
RASS	Richmond Agitation-Sedation Scale
SAE	Serious Adverse Event/Serious Adverse Experience
TDABC	Time-Driven Activity-Based Costing
TSA	Total Shoulder Arthroplasty

Title	Prospective, randomized clinical trial comparing analgesic efficacy of liposomal bupivacaine single-injection interscalene blockade to continuous interscalene blockade for patients undergoing primary total shoulder arthroplasty
Running Title	LB-SISB vs CISB
Protocol Number	21-000908
Phase	Phase IV
Methodology	Single center, unblinded, randomized control trial with two intervention arms
Overall Study Duration	14 Months (time when data collected for last patient)
Subject Participation Duration	Up to 7 days post-operatively
Single or Multi-Site	Single-Site
Objectives	Primary objective is to assess analgesia efficacy between liposomal bupivacaine single injection interscalene blockade vs. continuous interscalene nerve block for patients undergoing primary total shoulder arthroplasty. Secondary objectives include pain scores and opioid consumption at pre-defined time intervals, peripheral nerve block complications, length of hospital stay, and postoperative follow-up for up to 7 days after surgery depending on follow-up availability.
Number of Subjects	88 patients will be randomized to one of two interventions: liposomal bupivacaine single injection interscalene blockade or continuous interscalene nerve block.
Diagnosis and Main Inclusion Criteria	Patients presenting for unilateral primary total shoulder arthroplasty (includes anatomic and reverse total shoulder arthroplasty), who can provide consent, older than 18 years of age, and have American Society of Anesthesiologists (ASA) physiological status I-III.
Study Product, Dose, Route, Regimen	Liposomal bupivacaine (Exparel®). Patients will receive a one-time interscalene nerve block injection of 5 mL of bupivacaine 0.5% (25 mg) admixed with 10 mL of liposomal bupivacaine (133 mg).
Duration of Administration	One-time injection
Reference therapy	Continuous interscalene nerve block through an indwelling nerve catheter utilizing standard bupivacaine hydrochloride
Statistical Methodology	Randomization of each patient to a study arm will occur in a 1:1 allocation utilizing randomization schedule which will be created by the Division of Biomedical Statistics and Informatics. Subgroup analysis will be performed evaluating reverse total shoulder arthroplasty vs anatomic total shoulder arthroplasty, and patients who received allocated treatment per planned protocol

## 1 Introduction

This document is a clinical research protocol. The described study will be conducted in compliance with the protocol, Good Clinical Practices standards and associated Federal regulations, and all applicable institutional research requirements.

This document is a protocol for a human research study. This study will be carried out in accordance with the applicable United States government regulations and Mayo Clinic research policies and procedures.

Use of study medications within this study is not intended to be reported to the U.S. Food & Drug Administration (FDA) in support of a new indication for use or to support any other significant change in the labeling for the drug. Additionally, use of study medications within this study is not intended to support a significant change in the advertising for the product.

### 1.1 Background

Uncontrolled postoperative pain can be associated with significant deleterious consequences, including elevated stress response, decrease quality of life, increase in morbidity and mortality, and persistent post-surgical pain. Total shoulder arthroplasty (TSA) is considered to be a major surgical procedure resulting in severe postoperative pain, especially in the first 48 hours after surgery. In our recently published randomized clinical trial (IRB 15-009646; Mayo Clinic, Rochester, MN, USA), we reported that within a multimodal analgesic protocol, the continuous interscalene blockade (ISB) through an indwelling nerve catheter provides superior analgesia compared to single-injection interscalene blockade and local infiltration analgesia in the immediate postoperative period after primary TSA. Despite this, a few drawbacks to the continuous ISB include technical difficulty of catheter placement, increased procedure time, catheter dislodgement, leakage at the site of insertion, and developing an infrastructure to support the catheter.

Since our publication, liposomal bupivacaine, an extended-release bupivacaine formulation (currently marketed as Exparel®; Pacira Pharmaceuticals, Inc., Parsippany, New Jersey) had been approved by the FDA for use in single-injection ISB. Limited data has shown liposomal bupivacaine single-injection ISB to provide enhanced and prolonged analgesia compared to placebo and standard bupivacaine HCl single-injection ISB with a similar safety profile. There is a paucity of data comparing continuous-ISB (C-ISB) to liposomal bupivacaine single-injection ISB (LB-ISB) in a head-to-head clinical trial. Furthermore, the cost-effectiveness of either technique remains unknown in the context of the overall episode of care.

The primary aim of this study is to evaluate the analgesia efficacy between liposomal bupivacaine single injection interscalene blockade (LB-ISB) vs. continuous interscalene nerve block (C-ISB) for patients undergoing primary total shoulder arthroplasty.

## 1.2 Investigational Agent

Liposomal bupivacaine was approved by FDA in 2011 for surgical site infiltration and in 2018 for use in interscalene brachial plexus nerve blocks for postoperative pain control. Liposomal bupivacaine consists of vesicles of bupivacaine loaded in the aqueous chambers using DepoFoam® technology (Pacira Pharmaceuticals Inc, San Diego, CA). These vesicular liposomes will dissolve slowly and release bupivacaine over time, providing a longer analgesic effect than standard bupivacaine HCl. Chahar et al. provides a detailed review regarding liposomal bupivacaine's pharmacokinetics and molecular structure. Given the slow release of bupivacaine utilizing this unique DepoFoam® technology, analgesic effects can last up to 72 hours after a single injection into the surgical site.

Liposomal bupivacaine (Exparel®) is supplied in one vial, containing either 133 mg or 266 mg (1.3%; 13.3 mg/mL) of bupivacaine suspended in multivesicular liposomes in normal saline.

Bupivacaine HCl is an amide local anesthetic which inactivates voltage gated sodium channels. In nerves, this results in loss of action potential and signal conduction along the nerve fiber leading to sensory and/or motor blockade. Bupivacaine is a long-acting local anesthetic indicated for multiple routes of administration including local infiltration and peripheral nerve blocks.

## 1.3 Clinical Data to Date

### *Clinical Efficacy*

Most studies evaluating liposomal bupivacaine are limited to administration via surgical site infiltration; these clinical trials demonstrate prolong analgesia and decrease opioid consumption when compared to placebo in patients undergoing various surgical procedures. In contrast, analgesic outcomes were inconsistent when liposomal bupivacaine was compared to bupivacaine HCl for surgical site infiltration in total knee and hip surgery. Similarly, clinical trials evaluating interscalene nerve block with bupivacaine HCl compared to liposomal bupivacaine surgical site infiltration have shown variable analgesic outcomes.

Current data pertaining to the administration of liposomal bupivacaine via interscalene nerve blocks are sparse. Patel et al. reported significantly improved pain scores and reduced opioid consumption up to 72 hours postoperatively after comparing LB-ISB (utilized 133 mg of liposomal bupivacaine) to placebo ISB (using normal saline). Vandepitte et al. compared LB-ISB to ISB with standard bupivacaine HCl in patients undergoing major shoulder surgery. In the LB-ISB group, the authors admixed 5 mL of 0.25% bupivacaine HCl with 133 mg of

liposomal bupivacaine, while the control group received 15 mL of 0.25% standard bupivacaine HCl. The LB-ISB group had a moderate reduction in worst pain score in the first postoperative week compared to the control group (generalized estimating equation [GEE] estimated marginal mean values,  $3.6 \pm 0.3$  vs  $5.3 \pm 0.4$  points on the Numeric Rating Scale, difference,  $1.6 \pm 0.5$ ; 95% CI, 0.8–2.5).

Recently, a retrospective investigation evaluating LB-ISB vs C-ISB reported improved pain scores for LB-ISB on postoperative day (POD) 0 and 1, with similar opioid consumption and better cost efficiency compared to C-ISB. In the LB-ISB group, the authors prepared an injectate mixture composed of 10 mL of 0.5% bupivacaine HCl with 133 mg of liposomal bupivacaine. There were no complications noted in either group.

### *Safety*

In a meta-analysis, the safety profile of liposomal bupivacaine was similar to bupivacaine HCl. The most common side effects in the liposomal bupivacaine group (800 patients) were nausea (3.3%) and constipation (2.0%). Cardiac complications were tachycardia (4%), and bradycardia (2%), which did not require treatment and were similar to bupivacaine HCl group. One death was reported in the 800 patients that received liposomal bupivacaine, and one in the bupivacaine HCl group; both drugs were not deemed to be causative agents.

Ifeld et al. evaluated the safety of liposomal bupivacaine in peripheral nerve blocks (ankle, femoral nerve, and intercostal nerve block patients), and reported the most common adverse events to be mild in severity. These symptoms included nausea, pyrexia, constipation, vomiting, and pruritus. The incidence of central nervous system and cardiac adverse events were similar between liposomal bupivacaine, bupivacaine HCl, and placebo groups. The authors concluded that liposomal bupivacaine shares a similar safety profile to bupivacaine HCl and normal saline.

Patel et al. compared the interscalene nerve block with liposomal bupivacaine to normal saline and reported a similar incidence of adverse events between both groups. Most of the adverse events were considered mild in severity (nausea was the most reported adverse event). The authors performed pharmacokinetic assessments in patients receiving 166 mg and 266 mg of liposomal bupivacaine via interscalene block and reported peak concentrations occurring at 48 hours, with the mean peak concentrations (209 and 461 ng/mL, respectively) remaining below the thresholds for local anesthetic associated cardio- and neuro toxicity (2,000–4,000 ng/mL).

Similarly, in a clinical trial comparing LB-ISB to ISB with standard bupivacaine HCl, there were no increased risk of complications in the LB-ISB group (RR, 1.6; 95% CI, 0.9–2.7). Budge et al. reported no complications in their retrospective investigation comparing LB-ISB to C-ISB.

### *User Experience*

At our institution, liposomal bupivacaine has been used by our surgical colleagues for a variety of procedures (breast, hip, shoulder, knee, abdominal) without any reported side effects attributed to the medication. Furthermore, we have used liposomal bupivacaine for interscalene nerve block on numerous patients after FDA approval without any adverse events.

#### **1.4 Dose Rationale and Risk/Benefits**

##### **C-ISB group**

Patients will receive a loading dose of 15-20 mL bupivacaine HCl 0.5% followed by a continuous catheter infusion of bupivacaine 0.2% at 8 mL per hour for 72 hours. We have used this dose for many years in our practice, and we have successfully employed this in our previous randomized clinical trial. Further, this dose is commonly employed in studies involving interscalene blocks. These doses conform to the manufacturer recommended single and daily dose maximum administration and reliably provides postoperative analgesia.

##### **LB-ISB**

Patients will receive 5 mL of Bupivacaine HCl 0.5% (25 mg) mixed with 10 mL of liposomal bupivacaine (133 mg). This mixture is in accordance with manufacturer prescribing guidelines: max recommended dose of liposomal bupivacaine for interscalene nerve blocks is 133 mg and mixing dose ratio of standard bupivacaine HCl to liposomal bupivacaine of 1:2 or less (25 mg / 133 mg). Liposomal bupivacaine exhibits a bimodal plasma concentration profile, where an initial peak occurs at 1 hour and a second peak occurs between 12 to 36 hours. Therefore, adding standard bupivacaine HCl to liposomal bupivacaine will bridge the analgesic gap in the first few hours after the nerve block is performed. A similar administration mixture for interscalene blocks was used by Vandepitte et al.

## **2 Study Objectives**

### **2.1 Primary Objective**

To evaluate the analgesia efficacy in the first 24 hours postoperative period between liposomal bupivacaine single injection interscalene blockade and continuous interscalene nerve block via numeric rating pain score and opioid consumption for patients undergoing primary total shoulder arthroplasty.

### **2.2 Secondary Objective**

To evaluate the following: the analgesia efficacy between both groups up to 7 days postoperatively using numeric rating pain score assessment and opioid consumption, adverse events, duration of hospital stay, surgical recovery via quality of recovery questionnaire, and cost-benefit analysis via time-driven activity-based costing model.

Please refer to Section 3.2 and 3.3 for detailed outcome measures.

### **3 Study Design**

#### **3.1 General Design**

Single center, unblinded, randomized control trial with two intervention arms assessing acute pain management. These two arms include: 1) liposomal bupivacaine single-shot interscalene blockade (LB-ISB group) and 2) continuous interscalene nerve block (C-ISB group)

The study will be registered with [www.ClinicalTrials.gov](http://www.ClinicalTrials.gov)

After approval by Mayo Clinic IRB, we will work closely with the department of orthopedics at Mayo Clinic Hospital, Methodist Campus to enroll patients into the study. Potential subjects will consist of patients who present for elective primary TSA meeting the inclusion and exclusion criteria (Section 4.1 and 4.2). Subjects will be approached by study staff for recruitment in person and informed consent will be obtained during the preoperative clinic visit. Prior to surgery, subjects will be randomized to either one of the two study groups using dynamic allocation in a computer application developed by personnel in the Division of Biomedical Statistics and Informatics (Section 7.3). Subjects unable to give consent themselves will not be approached for participation. No remuneration will be provided. All efforts will be made to enroll participants regardless of ethnic heritage. No passive recruitment methods (newspapers, advertisements, or flyers) will be used.

Eighty-eight patients are required for this clinical trial. After baseline values are established, data will prospectively be collected during the peri-operative period up to 7 days post-operatively (patient will have follow-up via office visit or telephone call) for the purpose of this study. Data will be collected utilizing the institution's electronic medical record system and be transferred to an electronic research database (e.g. Excel, REDCap). Figure 1 and Table 1 summarizes the data that will be collected during this study.

Study Activity	Pre-	Peri- & Post-operative	
	operative	Pre-op	POD 0 (day of surgery)
Informed Consent	X		
Inclusion/Exclusion Criteria	X		
Pain Scores (numeric rating scale)	X	X	X
Patient and Surgical Data Collections	X	X	
OBAS			X
QoR-15 Patient Survey	X		X
Opioid Consumption		X	X
Length of Hospital Stay			X
Adverse Events Monitoring		X	X
Peripheral Nerve Block - catheter related complications		X	X
Follow up via telephone call or office visit		X	X*

Table 1. Summary of data collection

\*Patients may be contacted up to postoperative day 7 to collect data depending on availability of patient and study staff during follow-up encounters.

Office Visit

Study Recruitment  
Inclusion/exclusion criteria  
Discuss Study  
Consent  
  
74 Patients

Pre-OP

Randomize on Day of Surgery  
Dynamic Allocation  
  
1:1 LB-ISB vs. C-ISB

LB-ISB  
37 patients

C-ISB  
37 patients

Intra-OP

Shoulder Surgery

Post-OP

Postoperative Period  
Up to POD 7  
*(dependent on follow-up availability)*

- Capture:
- Pain Scores
  - Opioid Consumption
  - Length of Hospital Stay
  - Adverse Events
  - Quality of recovery Score
  - Overall Benefit of Analgesic Score
  - TDABC

Figure 1. Diagram of patient flow from recruitment to outpatient follow-up

### 3.2 Primary Outcome

To investigate the hypothesis that within our current multimodal analgesia total joint protocol, C- ISB provides superior analgesia via NRS pain intensity scores (difference  $\geq 1.5$ ) and opioid consumption (difference  $\geq 20$  mg oral morphine equivalents) on POD 1 compared to LB-ISB following primary total shoulder arthroplasty.

### 3.3 Secondary Outcomes

1. Pain intensity (NRS) assessments prior to surgery, post-anesthesia care unit (PACU), every 4 to 6 hours beginning on arrival to patient room (to the closet time interval), and hospital discharge up to POD 7.
2. Opioid consumption in daily oral morphine equivalents (OME) – preoperative, intraoperative, PACU stay, beginning on arrival to patient room up to POD 7.
  - a) Patients will be asked to record their daily intake of opioids and pain scores at pre-defined intervals. A research team member will follow-up with study patients to document the patient’s pain score and opioid consumption values for the previous day as well as administer the quality of recovery 15-item questionnaire.
3. Moderate to severe complications during regional anesthesia block placement (inadvertent epidural or subarachnoid injection, local anesthetic systemic toxicity\*, and pneumothorax).
 

*\* Local anesthetic systemic toxicity is suspected if a patient has acute onset of central nervous system changes (tinnitus, metallic taste in mouth, perioral numbness) or cardiovascular changes (bradycardia, hypotension, EKG changes).*
4. Peripheral nerve block catheter-related complications including presence of site infection (tenderness to palpation, erythema, swelling, drainage of pus), hematoma, and local anesthetic systemic toxicity.
5. Inadvertent catheter dislodgement
6. Duration of hospital stay (number of days), in addition to reason for hospital length of stay > 1 night (i.e., social work/disposition, inadequate pain control, nausea/vomiting, other)
7. Postoperative follow-up
  - a. Telephone encounter or office visit to collect NRS pain scores at rest, opioid consumption, questionnaire, and adverse events. Data will be collected for postoperative days 0 to 4; however, patients may be contacted up to postoperative day 7 to collect this information if patients or study staff are unavailable.
8. Questionnaire Forms
  - a) QoR-15
    - i. Quality of Recovery (QoR) 15-item short form patient survey is a validated, reliable, and feasible scoring system evaluating 5 dimensions of health: psychological support, comfort, emotions, physical independence, and pain.
    - ii. Collected preoperatively and POD 1 to 4 via office visit or telephone call.
  - b) Overall benefit of Analgesic Score (OBAS)
    - i. Validated tool measuring patient’s experience with their postoperative pain regimen. This simple 7 question (Q1 to Q7) scoring system entails a combination of pain intensity, adverse opioid events, and patient satisfaction. The total OBAS score is calculated via ‘sum items Q1 through Q6 and add [4 – score from Q7].’ This score consists of a 29-point scale ranging from 0

(best) to 28 (worst); therefore, lower OBAS scores indicate more analgesic benefit. This will be administered to patients prior to hospital discharge.

9. Cost-benefit analysis
  - a) Examining the cost of each analgesic modality within the overall episode of orthopedic surgical care using the time-driven activity-based costing (TDABC) model, which provides a more accurate representation of true costs by estimating the quantity of time and the cost per unit of time of each resource from preoperative visits to hospital discharge
10. Additional outcome measures for future investigation
  - a) American Shoulder and Elbow Surgeons Standardized Shoulder Assessment Form
    - i. ASES questionnaire will be collected pre-operatively, 3-month, and at 1 year postoperatively via office visit or telephone call. Collected data will be used in a follow-up study.
  - b) Patient-Reported Outcomes Measurement Information System (PROMIS®)
    - i. Already an established and standard questionnaire being collected for all orthopedic surgical patients.

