**Adverse Event Reporting Period**

For this study, the study treatment follow-up period is defined as up to 4 days following the last administration of study treatment.

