## 9.2 Recording of Adverse Events

The study team will seek information on adverse events by specific questioning and, as appropriate, by examination. This will occur on daily follow up inpatient encounters as well as telephone or office visit encounters up to 7 days post-procedure. Information on all adverse events will be recorded in the electronic medical record and in the appropriate adverse event worksheet. Related signs, symptoms, and abnormal diagnostic, laboratory or procedure results will be recorded as well. PI/Co-PI's will be notified of the adverse events.

The clinical course of each adverse event will be followed until resolution, stabilization, or until it has been determined that the study treatment or participation is not the probable cause. Serious adverse events that are still ongoing at the end of the study period will be followed, as stated above. Any serious adverse event that occurs after the study period and is considered related to the study treatment or study participation will be recorded and reported.

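### Pain and opioid outcomes are stated to POD 7 but collected only for POD 0 to 4, and the adverse-event period is defined three ways, one of which can differ in length between the arms

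*Combined protocol and SAP*

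**What the plan says.** **Pain and opioids.** Section 2.2 sets out to compare "the analgesia efficacy between both groups up to 7 days postoperatively using numeric rating pain score assessment and opioid consumption". In 3.3, outcome 1 takes pain scores to "hospital discharge up to POD 7" and outcome 2 takes opioid use from "beginning on arrival to patient room up to POD 7". Item 7a of the same section governs follow-up pain scores, opioid use, questionnaire and adverse events: "Data will be collected for postoperative days 0 to 4". It then adds that "patients may be contacted up to postoperative day 7 to collect this information if patients or study staff are unavailable". QoR-15 stops at POD 4. The synopsis and Figure 1 give follow-up to 7 days subject to availability, and the Table 1 footnote makes POD 7 a limit on contact. Section 3.1 describes data collection to 7 days.

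**Adverse events.** Item 7a includes them in the POD 0 to 4 data. The reporting period in 9.1 is "up to 4 days following the last administration of study treatment". Section 9.2 has them sought at daily inpatient encounters and at "telephone or office visit encounters up to 7 days post-procedure".

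**Treatment duration.** LB-ISB is a single preoperative injection (synopsis, 7.2). C-ISB is a loading dose followed by a planned 72-hour infusion (1.4, Figure 2).

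**The concern.** A secondary objective that runs to day 7 implies a day 7 comparison. If collection stops at POD 4, the plan promises a result that it has no scheduled data to produce. An analyst working from 2.2 and one working from item 7a would prepare different tables.

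For adverse events, a period counted from the last administration is not neutral when one arm is treated once and the other for up to three days. If 9.1 governs, C-ISB patients may be counted for longer than LB-ISB patients. Adverse events are part of the secondary objective. The stopping rules in 9.5 act at 5% of subjects per group and name no time window of their own.

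**Working it through.** **Figures not affected.** The plan's one computed design figure is 40 per arm. The NRS standard deviations in 8.1 combine to √((2.4² + 2.3²)/2) = 2.35. With a difference of 1.5 and two-sided alpha of 0.05, the t-test power at 40 per arm is 80.5%, so the figure reproduces. It concerns 24-hour outcomes and does not depend on the follow-up window.

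**Step 1: pain and opioid horizon.**

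| Source | Horizon | Role of POD 7 |
|---|---|---|
| 2.2 | 7 days | end of comparison |
| 3.3, outcomes 1 and 2 | POD 7 | end of outcome |
| 3.3, item 7a | POD 0 to 4 | last day to obtain the POD 0 to 4 data |
| Table 1 footnote | none stated | contact limit |
| 3.3, QoR-15 | POD 1 to 4 | none |

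Stated days minus collected days leaves POD 5, 6 and 7: 7 − 4 = 3 days with no planned collection. Section 8.2 names no time points for the secondary pain scores, so the statistical section does not settle which horizon applies.

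**Step 2: adverse-event period.** Take block placement as day 0. Let t be the C-ISB infusion time in hours, at most the planned 72. Under 9.1 the period ends at (day of last administration) + 4.

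- LB-ISB: 0 + 4 = day 4.
- C-ISB, if the end of infusion is the last administration: t/24 + 4.
- Gap between arms: t/24 days.

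| C-ISB last administration | C-ISB period ends | LB-ISB period ends | Gap (days) | Ratio of period lengths |
|---|---|---|---|---|
| Preoperative block only | day 4 | day 4 | 0 | 4/4 = 1.00 |
| Infusion ends at 24 h | day 5 | day 4 | 1 | 5/4 = 1.25 |
| Infusion ends at 48 h | day 6 | day 4 | 2 | 6/4 = 1.50 |
| Infusion ends at 72 h | day 7 | day 4 | 3 | 7/4 = 1.75 |

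The 24 h and 48 h rows are illustrations; the plan gives no distribution of infusion times. Item 7a (POD 0 to 4) and 9.2 (7 days from the procedure) each give a gap of 0, but they differ from each other by 3 days. Nothing says which of the three definitions prevails.

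**Step 3: where the period enters.** Section 8.2 tests intraoperative and in-hospital complications, a comparison bounded by discharge and not by 9.1. The period matters for adverse-event counts reported by arm and for 9.5. With 44 per arm (4.3.1), 2/44 = 4.5% and 3/44 = 6.8%, so the 5% threshold is crossed at 3 patients. Rule (c) is the most exposed: it covers unanticipated serious events and refers back to 9.1. The events in rule (a) arise at block placement.

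**The case against.** The strongest reply is that the plan follows both arms alike. Section 9.2 makes no distinction by arm in seeking events, and section 6 has study personnel follow every patient whatever the arm or hospital status. Section 9.1 does not say that the end of the infusion is the last administration. Section 7.5 treats the preoperative block as the only treatment needed, and section 7 describes only liposomal bupivacaine as study drug. On that reading both arms end on day 4 and 9.1 agrees with item 7a. This much stands: the unequal period depends on a reading that the plan leaves open, and staff who apply 9.2 uniformly would remove it. It does not settle the matter, because a continuing infusion is naturally read as continuing administration and 9.1 is the section that defines the reporting period.

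A reader might infer that C-ISB will show 1.75 times as many adverse events with no true difference. The documents do not support that. It needs the end-of-infusion reading, a full 72 hours in every patient and a constant event rate over the week. The plan itself expects some catheters to dislodge or occlude, and the serious events listed in 9.5 are tied to block placement or local anesthetic exposure, not to a flat hazard.

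On pain and opioids, the synopsis and Figure 1 make day 7 subject to availability, which suggests that a contact allowance was intended. That supports the correction, but 2.2 and outcomes 1 and 2 carry no such qualifier. A reader might also infer that POD 5 to 7 values would come from a selected, hard-to-reach subset. Item 7a does not say so: its late contacts are for POD 0 to 4 information. Outcome 2 also asks patients to record daily values, but its intervals are not given and item 7a schedules no collection beyond POD 4.

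**Conclusion.** Two inconsistencies stand and should be corrected.

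1. A 7-day pain and opioid comparison is stated, but collection is planned only for POD 0 to 4. Three days have no planned data, and no POD 5 to 7 comparison is supported.
2. Three adverse-event periods are given. Under 9.1 the arms differ by 0 to 3 days: 0 if only the preoperative block counts as administration, up to 3 if the end of a full 72-hour infusion does. The 7/4 ratio of period lengths is the upper case and serves as an illustration, not as an estimate of bias.

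Any distortion would fall on adverse-event counts reported by arm and on the stopping-rule counts, chiefly rule (c). The documents do not support extending it to the 24-hour primary outcomes, the sample size or the planned test of in-hospital complications.

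**What to change.** **Pain and opioids.** Restate 2.2 and outcomes 1 and 2 as POD 0 to 4, and describe POD 7 only as the last day on which those data may be obtained. Bring the synopsis, 3.1, Figure 1 and the Table 1 footnote into line. Do not present a POD 5 to 7 comparison.

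**Adverse events.** Put one period in 9.1, item 7a and 9.2, counted from block placement to the same day in both arms. Use day 7 if the 9.2 contacts will be made for every patient; otherwise use POD 4. Apply that period to the between-arm adverse-event summary and to the 9.5 counts. It governs counting only: the follow-up of unresolved events, and the recording of related serious events after the study period, already in 9.1 and 9.2, would stay as they are.

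**Cost.** Wording changes in several places and a shorter stated pain and opioid horizon. Choosing day 7 for adverse events adds a contact for any patient who would otherwise be last reached on POD 4; choosing POD 4 adds none but leaves later non-serious events out of the comparison.
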